1.0 Introduction

1.1 Background

Because of the potential for harmful effects, alcohol use is strongly discouraged in patients with liver disease. Alcohol abuse is common in patients with hepatitis C infection (1). In addition to the obvious potentiating effects of alcohol on liver injury, fibrosis and cancer in patients with chronic hepatitis C virus (HCV) infection, there is a well-known concurrent decrease of the effectiveness of interferon-based therapy (1 – 3). It has been previously shown that on-going alcohol intake inhibits the antiviral effects of interferon therapy of chronic hepatitis C (3). Even moderate levels of alcohol ingestion, associated with blood alcohol levels of 50 mg/dl, can impair the activity of interferon in HCV therapy. Alcohol abuse may increase liver enzymes but does not cause acute hepatic failure when medications, including LDV/SOF, are taken as prescribed. This study will monitor liver enzymes during LDV/SOF therapy. “Liver function” is poorly correlated with liver enzymes.

The effect of alcohol on the efficacy of direct-acting antivirals (DAAs) in HCV infection is poorly understood. Sofosbuvir is an oral, well-tolerated DAA with remarkable HCV polymerase inhibitor activity. Sofosbuvir-based therapy exhibits excellent inhibition of HCV replication in infected patients, raising the potential rate of a sustained viral response (SVR) to over 90%. Currently, the therapy of genotype 1 HCV infection with ledipasvir plus sofosbuvir in combination (LDV/SOV), results in an SVR in nearly 95% of naïve patients (4).

Ideally, the therapy of HCV-viremic drinkers should be to both cure the infection and cease alcohol use. Hepatitis C infection can be eradicated in the great majority of genotype 1 infected patients in as little as 8 to 12 weeks (4). The acquisition of sobriety is a typically a much more lengthy process that requires significant dedication and is often associated with relapses intermixed with periods of abstinence (5). The goal, therefore, should be to combine the therapies, acknowledging sobriety can take much longer to achieve than the drug cure of HCV. However, since HCV medications like LDV/SOV are very expensive, despite being cost-effective, insurers are delaying or denying alcoholic patients’ access to these DAAs at the present time. Currently, insurers may cite the identification of alcohol abuse as the reason to deny access to highly effective DAAs (5).

Protocol Version 3.0 01-Sep-2017, 2.0, 05-June 2017, version 1.0, 01-jan-2016,

The goal of this pilot study is to determine the effectiveness of LDV/SOV in genotype 1 HCV infected patients continuing to ingest alcohol.

1.2 Rationale

Approximately one-third of all HCV infected patients are presently or have been alcohol abusers or alcoholics. By eradicating the hepatitis C infection in alcohol abusers or alcoholics, these patients will have a reduced progression to cirrhosis and should reduce the risk of hepatocellular cancer (6).

2.0 Objectives and Endpoints

2.1 Primary Objectives:

- To determine the antiviral efficacy of LDV/SOF (SVR12) in alcoholics.
- To evaluate the safety and tolerability of LDV/SOF as assessed by review of the accumulated safety data.

2.2 Secondary Objectives:

- To assess HCV RNA at EOT, 12 weeks after therapy
- To assess the adherence of the LDV/SOF in subjects using a monthly calendar and monthly nursing assessment
- To assess changes in the QOL of the subjects from baseline to end of study with the CLDQ-HCV, SF-36 questionnaire and WPAI scores.

2.3 Primary Endpoints:

- The primary efficacy endpoint is SVR12 (HCV RNA <LLOQ 12 weeks after discontinuation of study drug).
- The primary safety endpoint is any AE leading to permanent discontinuation of study drug.

2.4 Secondary Endpoints:

- The proportion of subjects with HCV RNA < LLOQ at EOT

Protocol Version 3.0 01-Sep-2017, 2.0, 05-June 2017, version 1.0, 01-jan-2016,

- The adherence rates by pill count and attendance at monthly nurse visits changes in QOL scores (CLDQ-HCV, SF-36, WPAI) from baseline to end of study
- The proportion of patients who are able to complete therapy.

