3.3 Visit Schedule

All subjects will complete screening, on-treatment, and post-treatment assessments.

Screening assessments will be completed within 28 days of day 1 of starting therapy unless otherwise stated. Monthly nursing visits during therapy \pm 3 days, MD visits at screening, EOT, and 12 weeks after the last dose of therapy. See section 6.0 for detailed subject schedule.

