6.0 Procedures

Clinical Assessments	Day -28	monthly	EOT 13	Week 12 post	
	to Day 1	3 days \pm	-3 days up to + 4 weeks	-3 days up to + 4 weeks	
Informed Consent	X				
Audit -questionnaire	X	X	X	X	
WPAI, SF-36	X	X	X	X	
History & Physical	X		X	X	
Height, Weight	X		X	X	
Vital Signs	X		X	X	
Adverse Events	X	X	X	X	
CBC& WBC differential	X		X	X	
PT, INR	X				
Complete metabolic panel	X	X	X	X	
FIBRO Spect II Index PRN	X				
HCV RNA (within 6 months)	X		X	X	
Ultrasound abdomen (within 6 months)	X				
Fibroscan PRN	X				
Serum Pregnancy test PRN	X				
Urine Drug Screen	X				
Hepatis B surface antigen	X				
HIV panel	X				
Urinalysis	X				
Hemoglobin A1C	X				
Nursing/ Coordinator Visit		X	X	X	
Harvoni reconciliation (pill count)		X	X		
Medication \pm alcohol consumption diary	X	X	X	X	

Protocol Version 3.0 01-Sep-2017, 2.0, 05-June 2017, version 1.0, 01-jan-2016,

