6.2 Monthly Nursing/ Coordinator visits

Subjects will have a monthly visit with the nursing coordinator of the study \pm 3 days. This will be to assess drug adherence and accountability as well as to monitor for side effects and obtain alcohol consumption information we will also administer QOL questionnaires (WPAI, SF-36, Audit)

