6.3 Post Treatment Assessments

All subjects must complete the Post-Treatment EOT, and 12 week visit. For subjects who have completed an EOT, the post treatment 12 visit will be scheduled 12, after the last dose of therapy dose -3 days up to 4 weeks.

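### CLDQ-HCV is part of a secondary objective and endpoint, but the schedule of assessments does not collect it at any visit

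*Combined protocol and SAP*

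**What the plan says.** The secondary objective in section 2.2 is "To assess changes in the QOL of the subjects from baseline to end of study with the CLDQ-HCV, SF-36 questionnaire and WPAI scores". The matching endpoint in section 2.4 is "changes in QOL scores (CLDQ-HCV, SF-36, WPAI) from baseline to end of study". Both name three instruments and the same interval.

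On when assessments take place, section 3.3 says "See section 6.0 for detailed subject schedule". The section 6.0 table has four visit columns: Day -28 to Day 1, monthly, end of treatment (EOT), and week 12 post-treatment. Two of its rows are questionnaires. One is "Audit -questionnaire"; the other holds WPAI and SF-36. Each is marked in all four columns.

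Section 6.2 says that staff at the monthly visits will "administer QOL questionnaires (WPAI, SF-36, Audit"). Section 6.3 says "All subjects must complete the Post-Treatment EOT, and 12 week visit" and names no questionnaire.

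**The concern.** The objectives commit the study to a change score on CLDQ-HCV, while the schedule that sites work from has no entry for it. A change score needs two measurements per subject, and the table provides for neither. The baseline matters more: once a subject has started treatment, a pre-treatment score that was not taken is lost.

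A site that noticed section 2.2 and gave the form on its own initiative would have no scheduled visit for it, so its timing could differ between subjects. Either way, one stated component of a secondary endpoint would be missing or unevenly collected.

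**Working it through.** The plan gives no figure on this point, so the check sets the sections side by side and counts.

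**Step 1. Every place that could name or schedule a quality-of-life instrument.**

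| Section | CLDQ-HCV | SF-36 | WPAI |
|---|---|---|---|
| 2.2 objective | named | named | named |
| 2.4 endpoint | named | named | named |
| 6.0 table | absent | 4 of 4 columns | 4 of 4 columns |
| 6.2 monthly visits | absent | named | named |
| 6.3 post-treatment visits | absent | absent | absent |
| 8.3 analysis | absent | absent | absent |

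In the text supplied, CLDQ-HCV appears twice, both times in section 2.0.

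**Step 2. The table row by row.** It has 23 assessment rows. One holds WPAI and SF-36 and one holds AUDIT. The other 21 (23 - 2) are consent, examination, laboratory, imaging, adverse-event, visit, pill-count and diary entries. None names CLDQ-HCV, and AUDIT, which section 4.1 uses to define alcohol misuse, does not stand in for it.

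**Step 3. Time points needed for the change score.** Change = end-of-study score minus baseline score, so two are needed. Baseline is the Day -28 to Day 1 column. The documents do not define end of study; I take it as the last column, week 12 post-treatment.

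- SF-36 and WPAI: 2 of 2 time points scheduled.
- CLDQ-HCV: 0 of 2 scheduled.

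The CLDQ-HCV result does not depend on that choice, because the instrument is absent from all four columns.

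**Step 4. Could other text supply it?** Section 6.2 covers only the monthly visits, and its list omits the same instrument. Section 6.3 requires the EOT and 12-week visits but says nothing about questionnaires. Neither provides a baseline or an end-of-study CLDQ-HCV score.

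**The case against.** **Section 2.2 may be commitment enough.** It says the change is assessed with CLDQ-HCV, so a site might collect the form on that basis, or because the case report forms, which are not among the documents, include it. This stands in part: one cannot say that the data will be absent, only that the schedule does not provide for them. The two parts of the document still disagree.

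**Text may have been lost in conversion.** Numbering goes from 6.0 to 6.2 with no visible 6.1, and the table header is damaged. A lost passage cannot be fully excluded, but it is an unlikely explanation. The quality-of-life row is legible with all four marks, and the separate list in section 6.2 omits the same instrument.

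**End of study is undefined.** This is true, and section 7.2 collects adverse events up to a 24-week follow-up. It affects which visit the fix should name, but not the count of 0 in 4.

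**It is minor.** This is a single-arm pilot of 30 patients, section 8.3 sets out no analysis of quality-of-life change for any instrument, and no decision rests on CLDQ-HCV. That limits the weight of the point. What keeps it worth acting on is that a missed baseline cannot be recovered and the correction is very small.

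**Conclusion.** The inconsistency holds. CLDQ-HCV is named in both the secondary objective and the secondary endpoint, yet is scheduled in 0 of 4 visit columns, against 4 of 4 for SF-36 and WPAI. Followed as written, the schedule yields no CLDQ-HCV change score.

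The reach is one of three instruments within one secondary endpoint. SVR12, the safety endpoint, the sample size, SF-36 and WPAI are untouched. The sponsor should correct it, but it does not threaten the trial's main conclusion.

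The conclusion assumes that the section 6.0 table is the operative schedule, as section 3.3 indicates, and that no schedule text was lost in conversion.

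**What to change.** Choose one of two routes.

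1. **Keep the instrument.** Add CLDQ-HCV to the WPAI and SF-36 row in section 6.0, at least in the Day -28 to Day 1 column, completed before the first dose, and in the week 12 post-treatment column. State in section 2.4 that end of study means that visit, or name the visit intended and mark the form there. Add it to section 6.2 only if monthly scores are wanted.
2. **Drop the instrument.** Delete it from both section 2.2 and section 2.4.

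Keeping it costs one edit to a table row, one clarifying phrase, and one more questionnaire at two visits already held: 30 x 2 = 60 forms for the planned 30 subjects. If all 36 consented patients (section 8.2) completed it at screening and 30 completed it at the end, the total would be 36 + 30 = 66. Marking further columns would add to this. Dropping it costs two deletions. Neither route changes the sample size or the primary analysis.

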3.0 Study Design

3.1 Treatment Plan and Regimen

This is a single armed, open-labeled study to determine the efficacy and safety of LDV/SOF in treatment-naive alcoholic subjects with chronic genotype 1 HCV Infection either receiving 8 or 12 weeks of therapy as indicated by the FDA approved Harvoni label.

Projected Study Design: 52 weeks of screening and enrollment, 12 weeks of treatment, 12 weeks of follow-up.

N=30 patients.

3.2 Dose Modifications

There will be no dose modifications. If the subject has toxicities that are not tolerable it is advised to stop the therapy and the subject will be removed from the protocol.

3.3 Visit Schedule

All subjects will complete screening, on-treatment, and post-treatment assessments.

Screening assessments will be completed within 28 days of day 1 of starting therapy unless otherwise stated. Monthly nursing visits during therapy \pm 3 days, MD visits at screening, EOT, and 12 weeks after the last dose of therapy. See section 6.0 for detailed subject schedule.

4.0 Eligibility Criteria

4.1 Inclusion Criteria

1. The subject must be willingly and able to provide written informed consent
2. Age 19 years of age or older (The age of consent in Nebraska)
3. HCV treatment-naïve, as defined as no prior exposure to any Interferon (IFN), RBV, or other FDA approved or experimental HCV-specific direct-acting antiviral agent
4. HCV RNA level within 6 months prior to the Baseline/Day 1 visit.

Protocol Version 3.0 01-Sep-2017, 2.0, 05-June 2017, version 1.0, 01-jan-2016,

5. HCV genotype 1a, 1b, or mixed 1a/1b. Any non-definitive results will exclude the subject from study participation.
6. Alcohol misuse as defined by the Alcohol Use Disorders Identification Test (AUDIT) score subjects must score ≥ 8 (associated with harmful or hazardous drinking)
7. Cirrhosis determination
 - a) Cirrhosis is defined as any one of the following:
 - i) History of a liver biopsy showing cirrhosis (e.g. Metavir score = 4 or Ishak score ≥ 5)
 - ii) Fibroscan showing cirrhosis or results > 12.5 kPa
 - iii) FIBRO Spect II Index consistent with F3 or F4 AND an AST: platelet ratio index (APRI) of > 2 during screening)
 - b) Absence of cirrhosis is defined as any one of the following:
 - i) Liver biopsy within 2 years of Screening showing absence of cirrhosis
 - ii) Fibroscan within 6 months of Baseline/Day1 with a result of ≤ 12.5 kPa
 - iii) FIBRO Spect II Index consistent with F0- F2 AND APRI of ≤ 1 during Screening
8. Liver imaging (Abdominal Ultrasound) within 6 months of Baseline/Day 1 to exclude hepatocellular carcinoma HCC
9. Subjects must have the following laboratory parameters at screening:
 - a) ALT ≤ 10 x the upper limit of normal (ULN)
 - b) AST ≤ 10 x ULN
 - c) Bilirubin ≤ 2.0 x ULN
 - d) Platelets $\geq 50,000$
 - e) HbA1c $\leq 8.5\%$
 - f) Creatinine clearance (CLcr) ≥ 60 mL /min, as calculated by the Cockcroft-Gault equation
 - g) Hemoglobin ≥ 11 g/dL for female subjects; ≥ 12 g/dL for male subjects.
 - h) Albumin ≥ 2.5 g/dL
 - i) INR ≤ 1.5 x ULN unless subject has known hemophilia or is stable on an anticoagulant regimen affecting INR.
10. Subject has not been treated with any investigational drug or device within 30 days of the screening visit.

4.2 Exclusion Criteria

Protocol Version 3.0 01-Sep-2017, 2.0, 05-June 2017, version 1.0, 01-jan-2016,

1. Pregnant women and nursing mothers are ineligible due to the possible risk of adverse effects in the newborn. Eligible patients of reproductive potential should use adequate contraception if sexually active.
2. Serious concurrent medical illness which would jeopardize the ability of the subject to receive the therapy as outlined in this protocol with reasonable safety.
3. Malignancy diagnosed or treated within 5 years (recent localized treatment of squamous or non-invasive basal cell skin cancers is permitted; cervical carcinoma in situ is allowed if appropriately treated prior to screening); subjects under evaluation for a malignancy are not eligible.
4. Infection with hepatitis B virus (HBV) or human immunodeficiency virus (HIV)
5. Use of any prohibited concomitant medications within 30 days of the Baseline/Day 1 visit.
6. Known hypersensitivity to LDV/SOF

4.3 Subject Recruitment and Registration

All potential subjects who will be considered for this study will be evaluated in the internal medicine clinics at Nebraska Medicine. On initial presentation, a history and physical examination are performed, AUDIT questionnaire is obtained, as well as laboratory data. Additional studies will be obtained as clinically indicated. Patients who meet the eligibility criteria will be offered the opportunity to participate in this trial. The patient can then decide if they wish to participate. Before patients are enrolled into the study, an eligibility checklist must be completed to verify the subject meets the eligibility criteria. This will be signed by the investigator.

5.0 Drug Formulation and Procurement

5.1 Formulation

LDV/SOF is a fixed-dose combination tablet containing ledipasvir and sofosbuvir for oral administration. Ledipasvir is an HCV NS5A inhibitor and sofosbuvir is a nucleotide analog inhibitor of HCV NS5B polymerase.

Product: LDV/SOF fixed dose combination

Dose: 90/400 mg

Protocol Version 3.0 01-Sep-2017, 2.0, 05-June 2017, version 1.0, 01-jan-2016,

Frequency: Once daily

The tablets include the following inactive ingredients: colloidal silicon dioxide, copovidone, croscarmellose sodium, lactose monohydrate, magnesium stearate, and microcrystalline cellulose. The tablets are film-coated with a coating material containing the following inactive ingredients: FD&C yellow #6/sunset yellow FCF aluminum lake, polyethylene glycol, polyvinyl alcohol, talc, and titanium dioxide.

Ledipasvir: The IUPAC name for ledipasvir is Methyl [(2S)-1-{{(6S)-6-[5-(9,9-difluoro-7- {2- [(1R,3S,4S)-2-{{(2S)-2-[(methoxycarbonyl)amino]-3-methylbutanoyl}-2- Gilead Sciences 10 azabicyclo[2.2.1]hept-3-yl]-1H-benzimidazol-6-yl)-9H-fluoren-2-yl)-1H-imidazol-2-yl]-5- azaspiro[2.4]hept-5-yl}-3-methyl-1-oxobutan-2-yl]carbamate.

It has a molecular formula of C₄₉H₅₄F₂N₈O₆ and a molecular weight of 889.00. It has the following structural formula:

Ledipasvir is practically insoluble (<0.1 mg/mL) across the pH range of 3.0–7.5 and is slightly soluble below pH 2.3 (1.1 mg/mL).

Sofosbuvir: The IUPAC name for sofosbuvir is (S)-Isopropyl 2-((S)-(((2R,3R,4R,5R)-5- (2,4-dioxo-3,4-dihydropyrimidin-1(2H)-yl)-4-fluoro-3-hydroxy-4-methyltetrahydrofuran-2- yl)methoxy)-(phenoxy)phosphorylamino)propanoate. It has a molecular formula of C₂₂H₂₉FN₃O₉P and a molecular weight of 529.45. It has the following structural formula:

Sofosbuvir is a white to off-white crystalline solid with a solubility of ≥2 mg/mL across the pH range of 2–7.7 at 37°C and is slightly soluble in water.

5.2 Packaging and Labeling

HARVONI tablets are orange, diamond-shaped, film-coated, debossed with “GSI” on one side and “7985” on the other side of the tablet. Each bottle contains 28 tablets (NDC 61958-1801-1), a silica gel desiccant, polyester coil, and is closed with a child-resistant closure.

5.3 Storage and Handling

Store at room temperature below 30°C (86°F).

5.4 Dosage and Administration

Each tablet contains 90 mg ledipasvir and 400 mg sofosbuvir. The tablet is to be administered once daily and can be taken with or without food. Subjects should maintain the same daily dosing interval between doses.

When a dose of study medication is missed the subject should be instructed to take the dose as soon as possible during the SAME day. Subjects should NEVER double the next dose.

5.5 Study Drug Adherence and Drug Accountability

Protocol Version 3.0 01-Sep-2017, 2.0, 05-June 2017, version 1.0, 01-Jan-2016,

Subjects will be instructed to bring back the bottle of study medication in the original container at each monthly visit. The medication will be reconciled using a pill count at each monthly visit. This will serve as the subject's adherence with the study medication.

Subjects must also bring the medication/ alcohol consumption diary data to each visit.

Subject's diary will include subject's record of missed doses during the month and estimated number of daily drinks (the number of drinks per day and the number of grams per day) for the month.

5.6 Concomitant Medications

H2-receptor antagonist must not exceed a dose of 20mg of omeprazole or equivalent. Antacids that directly neutralize stomach pH may not be taken within 4 hours of study drug administration.

The following medications are prohibited from 30 days prior to the Baseline/Day 1 visit Throughout the end of treatment, or otherwise specified:

- amiodarone (Cordarone[®], Nexterone[®], Pacerone[®]) within 3 months
- carbamazepine (Carbatrol[®], Epitol[®], Equetro[®], Tegretol[®])
- digoxin (Lanoxin[®])
- efavirenz, emtricitabine, tenofovir disoproxil fumarate (ATRIPLA[®])
- elvitegravir, cobicistat, emtricitabine, tenofovir disoproxil fumarate (STRIBILD[®])
- oxcarbazepine (Trileptal[®], Oxtellar XR[®])
- phenytoin (Dilantin[®], Phenytek[®])
- phenobarbital (Lumina
- phenobarbital (Luminal[®])
- rifabutin (Mycobutin[®])
- rifampin (Rifadin[®], Rifamate[®], Rifater[®], Rimactane[®])
- rifapentine (Priftin[®])
- rosuvastatin (Crestor[®])
- simeprevir (Olysio[®])
- St. John's wort (*Hypericum perforatum*) or a product that contains St. John's wort
- tipranavir (Aptivus[®]) used in combination with ritonavir (Norvir[®])
- tenofovir disoproxil fumarate (VIREAD[®], TRUVADA[®]) used in combination with atazanavir (Reyataz[®]) and ritonavir (Norvir[®]), darunavir (Prezista[®]) and ritonavir (Norvir[®]), or used in combination with lopinavir and ritonavir (Kaletra[®])

Protocol Version 3.0 01-Sep-2017, 2.0, 05-June 2017, version 1.0, 01-jan-2016,

Protocol Version 3.0 01-Sep-2017, 2.0, 05-June 2017, version 1.0, 01-jan-2016,

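### Section 5.6 sets the limit for H2-receptor antagonists by a dose of omeprazole, a proton-pump inhibitor, so the class and the reference drug do not match

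*Combined protocol and SAP*

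**What the plan says.** Section 5.6 (Concomitant Medications) opens with two sentences on acid-reducing drugs. The first is "H2-receptor antagonist must not exceed a dose of 20mg of omeprazole or equivalent". The second is "Antacids that directly neutralize stomach pH may not be taken within 4 hours of study drug administration". A list of prohibited drugs follows, running from amiodarone to the tenofovir combinations.

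Four other places bear on the point:

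- Exclusion criterion 5 in section 4.2 bars "Use of any prohibited concomitant medications within 30 days of the Baseline/Day 1 visit".
- Section 5.4 sets the dosing instructions, including "The tablet is to be administered once daily and can be taken with or without food".
- Section 3.1 mentions the product label when it describes subjects "either receiving 8 or 12 weeks of therapy as indicated by the FDA approved Harvoni label".
- Section 5.1 says: "Ledipasvir is practically insoluble (<0.1 mg/mL) across the pH range of" 3.0 to 7.5. It gives a solubility of 1.1 mg/mL below pH 2.3.

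**The concern.** The sentence is an operative rule: staff and subjects are meant to apply it throughout treatment. It cannot be applied as written, because the named class and the drug that defines the dose belong to different classes. Someone asked whether a given H2 antagonist at a given dose is permitted would find no answer in the protocol. Someone asked about a proton-pump inhibitor would have to decide whether the sentence applies to that class at all.

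What is at stake is drug exposure. The protocol's own solubility figures show that ledipasvir dissolves better in a more acid environment, and the protocol evidently regards acid reducers as needing control, since it restricts them. A rule that can be read as permitting unlimited use of one class or the other could allow acid suppression that plausibly lowers ledipasvir exposure, in a trial whose primary efficacy endpoint is SVR12.

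**Working it through.** There is no figure to reproduce and no formula applies. The check is to read the sentence both ways, see what each reading leaves open, and then look for a passage that closes the gap.

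**Input from outside the documents.** That omeprazole is a proton-pump inhibitor is general pharmacology. The documents do not state it.

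**The two readings of the sentence in section 5.6**

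| Reading | Proton-pump inhibitors | H2-receptor antagonists |
|---|---|---|
| Literal: the cap applies to H2 antagonists | No limit anywhere in the text | Capped, but in units of another class's drug; no conversion is given, so there is no usable dose |
| Cap assigned to the wrong class: it was meant for proton-pump inhibitors | Capped at omeprazole 20 mg or equivalent | No limit anywhere in the text |

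The second reading is the more plausible. A dose of omeprazole with an equivalence clause makes sense as a limit within omeprazole's own class, and makes little sense as a limit on a different class. Even so, it leaves the class that the sentence names without a limit.

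**Places that might supply the missing part**

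1. The antacid sentence in section 5.6 is confined to agents that neutralize stomach acid directly, so it reaches neither class.
2. The prohibited list in section 5.6 names no proton-pump inhibitor and no H2 antagonist.
3. Exclusion criterion 5 in section 4.2 refers only to prohibited medications, so it adds nothing beyond that list.
4. Section 5.4 covers food, the dosing interval and missed doses. It does not mention acid reducers.
5. Section 3.1 cites the label for the 8- or 12-week duration. It does not import the label's rules on concomitant medication.

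None of the five closes the gap under either reading.

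**Why the rule bears on exposure.** Section 5.1 gives ledipasvir solubility as 1.1 mg/mL below pH 2.3 and less than 0.1 mg/mL from pH 3.0 to 7.5. Solubility therefore falls as pH rises, which gives a qualitative reason for limiting acid suppression.

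**What is not touched.** Section 8.2 rests on 30 patients and an anticipated proportion of 0.92. Section 8.3 plans a proportion with a 95% confidence interval. Neither uses anything from section 5.6.

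**The case against.** The strongest reply is that this is a slip of drafting that any hepatology clinic would see through. Recruitment is described at one centre, which can settle on one reading; the more plausible reading does cap proton-pump inhibitors; and the drug has a label that staff can consult. Much of this stands, and it is why the point is minor. It does not dispose of the point, because staff who infer the proton-pump-inhibitor cap still cannot find an H2-antagonist dose in this text. If they take one from the label, they are following a rule that the protocol does not contain.

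Three stronger readings are tempting, and the documents do not support them:

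- A reader might infer that the trial leaves proton-pump inhibitors unrestricted. That follows only from the literal reading, which is the less plausible one.
- A reader might infer from the 4-hour antacid separation that H2 antagonists and proton-pump inhibitors each need a timing rule, and that its absence is a further error. The antacid rule concerns direct neutralizers and shows nothing about the other two classes. Whether they need a timing rule is a matter for the label, which is not in the documents.
- A reader might take the gap between 1.1 and less than 0.1 mg/mL as the size of the harm. Those figures describe solubility at given pH values. The documents say nothing about gastric pH on an acid reducer, the resulting ledipasvir exposure, or the response.

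**Conclusion.** The mismatch between class and reference drug is real and is not corrected elsewhere. Under either reading, one of the two classes has no limit; under the literal reading, the other also has no usable dose. Confidence in this is high, and it rests on one outside fact, the class to which omeprazole belongs.

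The effect on exposure is plausible from section 5.1, but neither it nor any effect on SVR12 can be quantified from the documents. The sample size and the planned analysis stand as they are. This is a minor operational correction, worth considering because it is cheap and concerns a rule in daily use during treatment.

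**What to change.** Replace the first sentence of section 5.6 with two limits, one for each class:

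- Proton-pump inhibitors: no more than omeprazole 20 mg or an equivalent dose.
- H2-receptor antagonists: no more than a stated dose of a named H2 antagonist, or its equivalent.

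The sponsor should check both limits against the product label, and add a timing rule for either class if the label calls for one. The H2-antagonist dose cannot be supplied from the documents. The antacid sentence should stay as it is.

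The cost is one sentence becoming two. A subject taking more than the corrected cap would need a dose change. No new visit, test or analysis is required.
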